**Table 3-4. Analysis Visit Windows for Hematology, Coagulation and Chemistry Laboratory Tests**

Nominal Visit	Nominal Study Day	Visit Window Study Day	
		Lower Limit	Upper Limit
Baseline	1	(none)	1 (Pre Dose)
Day 3	3	1 (Post Dose)	4
Day 7	7	5	9
Day 14	14	10	(none)

FLU-PRO Plus Questionnaire were to be collected daily from Day 1 through Day 14; therefore, windows are not assigned and results will be summarized for each Study Day.

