    - Symptoms scored as 2 or higher at baseline are scored as 0 or 1 at postbaseline, AND
    - Symptoms scored as 1 at baseline are scored as 0 at postbaseline, AND
    - for two consecutive days.
  - Time to alleviation of baseline COVID-19 symptoms is defined (in days) as:

First Date of the two consecutive dates achieving alleviation - First dose Date + 1

If a participant has not achieved symptom alleviation at last FLU-PRO Plus assessment or early discontinuation of study, the participant will be censored at last FLU-PRO Plus assessment date. Last assessment date is the last date when at least one of the baseline symptoms is assessed.
- Worsening after alleviation of baseline COVID-19 symptoms
  - The worsening after alleviation of baseline COVID-19 symptoms is defined as:
    - For a participant who has achieved alleviation of baseline COVID-19 symptoms
    - If any symptom scored as 2 or higher at baseline is scored as 2 or higher postbaseline after achieved alleviation, or
    - Any symptom scored as 1 at baseline are scored as 1 or higher postbaseline after achieved alleviation.
- Proportion of participants progressing to requiring oxygen supplementation by Day 28

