### 6.2.1. Analysis of Secondary Endpoints

The FAS will be the primary analysis set for secondary endpoints. The mFAS will be used for secondary endpoints of composite endpoint of COVID-19 related MAVs or death.

All-cause mortality by Day 28 will be compared between the 2 treatment groups using the Fisher exact test. If a participant prematurely discontinues from the study prior to Day 28 or the Death status is missing, the participant will not be included in the analysis.

The secondary endpoint of COVID-19 related hospitalization or all-cause death by Day 14, COVID-19 related MAVs or death by Day 28, and COVID-19 related MAVs or death by Day 14 will be analyzed using the same method as used for the primary endpoint, described in Section 6.1.3.

The proportion of participants hospitalized (COVID-19 related) by Day 28 will be estimated using the Kaplan-Meier method and compared between the 2 treatment groups using a log-rank test. Hazard ratio and two-sided 95% CI estimated using the Cox regression with baseline stratification factors as covariates will be provided.

Number and percentage of participants progressing to requiring oxygen supplementation by Day 28 will be summarized and compared between treatment groups using the Fisher Exact test. Participants discontinued from the study before progressing to requiring oxygen supplementation will be considered as not requiring oxygen supplementation.

The Kaplan-Meier product limit method will be used to estimate and log-rank test will be used to compare treatment groups for the time to alleviation of baseline COVID-19 symptoms. Hazard ratio and two-sided 95% CI estimated using the Cox regression with baseline stratification factors as covariates will be provided. Number and proportion of participants with worsening after alleviation of baseline COVID-19 symptoms will be summarized.

Time-weighted average change in SARS-CoV-2 viral load from baseline to Day 7 will be summarized by treatment groups and compared between treatment groups using an ANCOVA model with baseline viral load as covariate, the analysis will be based on the Virology Analysis Set.

CC1

[REDACTED]

[REDACTED]

[REDACTED]

[REDACTED]

[REDACTED]

[REDACTED]

[REDACTED]

[figure not shown]
[REDACTED]

[REDACTED]

CCI

CCI

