#### **Events with Completely Missing Onset Date**

An AE with a completely missing onset date is defined as TEAE if end date meets any of the 3 criteria specified above.

- 10) The precision in reporting numerical values should be as follows:

Raw measurements will be reported the same as the data captured electronically or on the eCRF for all but hematology and chemistry values.

Standard deviation and standard error will be reported to one more significant decimal place than the raw measurement.

Mean, median, minimum, Q1, Q3, and maximum will be reported to the same number of decimal places of the raw measurements.

Exceptions may be considered; for example, if more than 4 significant digits are provided for the measurement.

Precision for derived parameters as follows:

Parameters	Decimal Places
log 10 of SARS-CoV-2 viral load	2
Time-weighted average change in SARS-CoV-2 viral load	2
BMI	2
CCI	

- 11) Last dose date is not expected to be missing. However, if last dose date is missing, it will be imputed using the maximum of non-missing, non-zero dose, study drug start and stop dates.
- 12) Incomplete death dates will be imputed as the maximum of the study drug start dates, study drug end dates, clinic or phone visit dates (lvis28dt), laboratory visit dates (llab28dt), including the 28-day follow-up visit date plus 1.
- 13) Censoring rules

Time to hospitalization/death: If a participant prematurely discontinues from the study prior to Day 28 or the hospitalization status is missing, the participant is censored at last study date or day 28 whichever is earlier.

Time to negative SARS-CoV-2 viral load, participants are censored at the last assessment day and participants are required to have at least one postbaseline assessment.

Time to alleviation of baseline COVID-19 symptoms:

- For overall baseline symptom alleviation, participants are censored at the last assessment day that at least one of the baseline symptoms was assessed. For baseline symptom alleviation for each domain, participants are censored at the last assessment day that at least one of the baseline symptoms within that domain was assessed

- 14) Graded Laboratory Abnormalities Summary

The following labels will be used for laboratory abnormalities and Grade 3 or 4 laboratory abnormalities summary tables and listings:

Battery	Lab Test Label Used in I-labtox Listing	Toxicity Direction	Lab Test Label Used in t-labtox Table
Hematology	Hemoglobin	Decrease	Hemoglobin (Decreased)

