## 18) Symptom alleviation and time to baseline symptom alleviation

1. Baseline symptoms: Baseline symptoms are the symptoms collected prior to dosing and score  $\geq 1$ .
  - Item 1 to 34 of the FLUPRO are symptoms. Global assessments (last 6 items in the questionnaire) are not symptoms.
  - Each subject's baseline symptoms including number of symptoms likely are different.
  - For alleviation of baseline symptoms, only need to follow the symptoms presented ( $\geq 1$ ) at baseline
    - If a participant has 5 baseline symptoms, only the 5 symptoms will be followed to derive alleviation.
    - If a symptom (e.g. coughing) is not one of the baseline symptoms and has a score  $>1$  post baseline, the symptom will be not considered to derive the subject's baseline symptom alleviation.
    - If participant has not symptom  $\geq 1$  at baseline, alleviation status for the participant is missing for all visit.
    - Baseline symptoms  $\geq 1$ , symptoms from Day 2 and later are all missing, the alleviation status for the symptom is missing for all visits.
2. Alleviation of a symptom:
  - Symptom scored as 2 or higher at baseline are scored as 0 or 1 at postbaseline
  - Symptom scored as 1 at baseline are scored as 0 at postbaseline

- for two consecutive days - need to be confirmed with 2 visits
  - one missing day between two visits (that meets the alleviation definition) is allowed, but 2 or more days of missing is not considered reach alleviation
  - for Day 14 (or last assessment on Day x), if the symptom meets definition of alleviation, and day 13 (or Day x -1) also meets the definition of alleviation, then it is considered as confirmed. One missing day is allowed for the confirmation of Day 14 or last assessment, i.e if day 13 (or Day x-1 ) is missing and Day 12 (or Day x-2) meets the definition of alleviation, then it is considered as confirmed.

Examples:

Example	Day														Alleviation for a symptom on day	
	1	2	3	4	5	6	7	8	9	10	11	12	13	14		
1	2	2	2	1	1	1	0	0	0	0	0	0	0	0	4	baseline 2 or higher needs to be 1 or 0
2	2	2	2	0	1	1	0	0	0	0	0	0	0	0	4	baseline 2 or higher needs to be 1 or 0
3	2	2	2	0	2	1	1	0	0	0	0	0	0	0	6	day 4 is not confirmed
4	3	2	2	1	1	1	0	2	1	1	0	0	0	0	4	still on day 4 if worsen after confirmation
5	1	1	1	0	0	0	1	0	1	1	0	0	0	0	4	Worsening on day 7
6	1	1	1	1	0	0	0	0	0	0	0	0	0	0	5	baseline 1 needs to be 0
7	2	2	2	1	.	1	0	0	0	0	0	0	0	0	4	allow one missing

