### 3. Alleviation of baseline symptoms for a participant

The alleviation status for a participant at each visit is

- Yes, if all confirmed baseline symptom alleviation status are Yes.
- if > 25% of symptoms are missing, then alleviation status is No, else ignore missing.
- No, if any baseline symptom alleviation status is No.

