#### 4. Tim to alleviation of baseline symptoms

First day of participant level alleviation status equals Yes. If a participant has not achieved symptom alleviation at last FLuPRO assessment, the participant will be censored at the date of last FLUpro assessment. For symptom alleviation of a domain, the last assessment date is only among those baseline symptoms within the domain.

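### Time to symptom alleviation: trailing diary days too incomplete to register alleviation still extend follow-up and count as known non-alleviation, even when every answered symptom has resolved

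*SAP*

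**What the plan says.** Time to alleviation is a secondary endpoint (protocol 3.1, SAP 6.2). SAP 3.5 classes every efficacy endpoint other than the primary as exploratory. SAP 6.2.1 states: "The Kaplan-Meier product limit method will be used to estimate and log-rank test will be used to compare treatment groups". A Cox hazard ratio is added. The diary runs daily: "FLU-PRO Plus Questionnaire were to be collected daily from Day 1 through Day 14".

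- **Event.** Appendix 2 item 18.4: "First day of participant level alleviation status equals Yes".
- **Status on a partly answered day.** Item 18.3: "if > 25% of symptoms are missing, then alleviation status is No, else ignore missing". A further line of 18.3 gives No if any baseline symptom is itself not alleviated.
- **Censoring.** Item 13: "For overall baseline symptom alleviation, participants are censored at the last assessment day that at least one of the baseline symptoms was assessed". SAP 6.2 agrees: "Last assessment date is the last date when at least one of the baseline symptoms is assessed".
- **A looser wording.** In item 18.4, a participant without alleviation is handled so that "the participant will be censored at the date of last FLUpro assessment". For the overall endpoint this is not limited to baseline symptoms.
- **Gaps.** Item 18.2 lets a symptom's confirmation bridge one missing day, "but 2 or more days of missing is not considered reach alleviation".

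**The concern.** The event rule and the censoring rule use different standards of completeness. To register alleviation, a day needs at least 75% of symptoms answered. To count as follow-up, it needs one answer. A day between these standards adds time at risk and cannot produce an event.

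This matters on trailing days when every answered baseline symptom meets the alleviation criterion. The unanswered items may or may not have resolved, so the participant's status is undetermined, yet the analysis treats it as known non-alleviation.

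The SAP handles missing information differently elsewhere. Wholly blank trailing days do not extend follow-up (item 18.2, examples 10 and 12). Item 18.1 uses missing as an alleviation status when all later data for a symptom are absent. Item 17 calculates no domain score when too few items are answered, rather than assigning a poor one. No visible sensitivity analysis covers partly completed diaries; SAP 6.1.4 concerns the primary endpoint only.

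**Working it through.** **1. Reproducing the SAP's own examples.** The single-symptom rule was coded: baseline 2 or more falling to 0 or 1, or baseline 1 falling to 0; confirmed at the next visit with one missing day allowed; otherwise censored at the last answered day. It reproduces 12 of the 13 worked examples, including the censored ones (example 9, Day 14; example 10, Day 13; example 12, Day 9). In example 11 the scores as extracted first qualify on Day 12, while the table states Day 13. That may be an extraction fault and does not bear on this point.

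**2. When the mismatch can arise.** It needs at least one answer and a missing fraction above 0.25. Taking the denominator as the participant's baseline symptoms:

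| Baseline symptoms | Fewest unanswered items that trigger it |
|---|---|
| 1 | cannot arise |
| 2 or 3 | 1 (1/2 = 50%, 1/3 = 33%) |
| 4 to 7 | 2 (1/4 = 25% is not above 25%) |
| 8 | 3 (2/8 = 25% is not above 25%) |
| 12 | 4 (3/12 = 25% is not above 25%) |

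Item 18.3 does not state the denominator. If it were all 34 items, 0.25 × 34 = 8.5, so 9 unanswered items would be needed.

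**3. Constructed profiles (not trial data).**
- Eight baseline symptoms scored 2, complete and unchanged to Day 6. On Days 7 to 14, five of eight are answered, all 0 (3/8 = 37.5% missing). The SAP gives no event and censors at Day 14. The last determinable day is Day 6, so 14 − 6 = 8 undetermined days count as non-alleviation.
- Two baseline symptoms, both first alleviated on Day 4 but unconfirmed, then one of two answered and resolved. The SAP censors at Day 14; the last determinable day is Day 4.
- The first profile again, but with one of the five answered symptoms still at 2 through Day 14. Status is then known to be No, and Day 14 is the correct censoring day.

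**4. Direction.** The Kaplan-Meier proportion alleviated is 1 − ∏(1 − d/n) over event days, with d events and n at risk. Changing No to missing alters no Yes day, so d is the same under every censoring rule considered here. Later censoring raises n and lowers the estimate. The last determinable day is never later than the SAP's date and never earlier than the last day with at least 75% answered. Its estimate must therefore lie between those two.

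**5. Size under assumed values, switching to partial diaries independent of recovery.** Daily alleviation probability 0.08 on placebo and 0.11 on RDV; switch on a random day from 3 to 13 and partial thereafter; 20,000 simulated per arm. With confirmation needed, alleviation must start on Days 2 to 13, so the true placebo value is 1 − 0.92^12 = 63%. The true rate ratio is ln(0.89)/ln(0.92) = 1.40.

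| Switching, placebo / RDV | Placebo alleviated by Day 14, SAP | Same, last day with at least 75% answered | Rate ratio, SAP | Rate ratio, 75% rule |
|---|---|---|---|---|
| 5% / 5% | 61.7% | 63.2% | 1.37 | 1.37 |
| 10% / 10% | 60.0% | 62.9% | 1.39 | 1.39 |
| 20% / 20% | 56.8% | 62.2% | 1.39 | 1.40 |
| 30% / 30% | 54.0% | 62.0% | 1.37 | 1.39 |
| 20% / 10% | 57.2% | 62.8% | 1.49 | 1.40 |
| 10% / 20% | 60.3% | 63.0% | 1.28 | 1.38 |

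**6. Does the reason for partial diaries matter?** Assumed 7% daily, no confirmation day, Days 2 to 14: truth 1 − 0.93^13 = 61%. A 20% share switches.

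| Who switches | SAP rule | 75% rule |
|---|---|---|
| Anyone, on a random day | 55% | 61% |
| Participants, on the day they recover | 49% | 53% |
| Only those not recovered by Day 14 | 61% | 65% |

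By step 4, the last-determinable-day rule lies between the columns. In the second row it equals 53%, because every answered item is resolved from the switch onward. In the third it equals 61%, provided an answered item shows the persisting symptom. In the first it corrects only partly: someone who switches before recovering stays at risk until the answered items resolve and is censored there.

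**The case against.** The SAP rule is a prespecified, coherent convention: insufficient evidence of alleviation counts as not alleviated, and the day was assessed. A reader might infer that the two rules contradict each other. They do not; a day scored No is a scored day.

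A reader might also infer that status is unknown on every day with more than 25% missing. Item 18.3 shows otherwise: one answered symptom still above threshold settles the matter as No. For the same reason, replacing the SAP date outright with the last day at least 75% complete would discard documented persistence. The third row of step 6 shows the cost, 65% against a true 61%. Nor does that replacement cure the problem if people stop answering because they have recovered: it closes (53 − 49)/(61 − 49), a third of the gap.

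A third tempting inference is that the treatment comparison is biased. With equal rates the ratio barely moves, and nothing in the documents suggests unequal rates in a double-blind trial with matched placebo.

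Finally, a reader might carry the 75% requirement into each domain. Item 18.3 is written at participant level. Item 17 accepts 1 of 2 Sense items and 2 of 3 Throat items for domain scores; 75% would demand 2 of 2 and 3 of 3 if all were baseline symptoms.

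These objections narrow the point but leave its core: on trailing partial days with only resolved answers, the plan asserts a status it cannot know.

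**Conclusion.** The point holds for trailing, partly answered days on which more than 25% of baseline symptoms are blank and every answered one meets the alleviation criterion. Such days become event-free follow-up, which lowers the proportion alleviated and lengthens apparent time to alleviation. Bias in the hazard ratio needs partial-diary rates that differ by arm, and its direction then depends on which arm has more.

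The true size is unknown, because the documents report no rate of partial diaries. The figures above rest on assumed hazards, assumed switching shares and partial diaries persisting to Day 14. If diary entry forces complete answers, the effect is nil. Wholly blank trailing days are already handled, and a single gap can be bridged. The endpoint is exploratory and the primary conclusion is unaffected. Alignment is worthwhile because it costs little and SAP section 1 places finalization of the plan before database finalization.

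**What to change.** In SAP 6.2 and Appendix 2 items 13, 18.3 and 18.4:

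1. Keep No whenever any answered baseline symptom is still unalleviated.
2. Set status to missing when more than 25% of baseline symptoms are unanswered and all answered ones meet the criterion.
3. Censor at the last day with determinable status, and use that one definition of the last assessment date throughout.
4. State that the 25% refers to the participant's baseline symptoms.
5. As a sensitivity analysis, censor at the last day with at least 75% of baseline symptoms answered. With step 4 of the working, this shows how far the result depends on partial diaries.
6. Do not extend the 75% requirement to domains.

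Reporting partial-diary days by arm would show whether the issue matters in practice.

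The cost is a few lines of wording and derivation code. Some participants are censored earlier, and censoring may still be informative if people stop answering items because they have recovered.

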## 18) Symptom alleviation and time to baseline symptom alleviation

1. Baseline symptoms: Baseline symptoms are the symptoms collected prior to dosing and score  $\geq 1$ .
  - Item 1 to 34 of the FLUPRO are symptoms. Global assessments (last 6 items in the questionnaire) are not symptoms.
  - Each subject's baseline symptoms including number of symptoms likely are different.
  - For alleviation of baseline symptoms, only need to follow the symptoms presented ( $\geq 1$ ) at baseline
    - If a participant has 5 baseline symptoms, only the 5 symptoms will be followed to derive alleviation.
    - If a symptom (e.g. coughing) is not one of the baseline symptoms and has a score  $>1$  post baseline, the symptom will be not considered to derive the subject's baseline symptom alleviation.
    - If participant has not symptom  $\geq 1$  at baseline, alleviation status for the participant is missing for all visit.
    - Baseline symptoms  $\geq 1$ , symptoms from Day 2 and later are all missing, the alleviation status for the symptom is missing for all visits.
2. Alleviation of a symptom:
  - Symptom scored as 2 or higher at baseline are scored as 0 or 1 at postbaseline
  - Symptom scored as 1 at baseline are scored as 0 at postbaseline

- for two consecutive days - need to be confirmed with 2 visits
  - one missing day between two visits (that meets the alleviation definition) is allowed, but 2 or more days of missing is not considered reach alleviation
  - for Day 14 (or last assessment on Day x), if the symptom meets definition of alleviation, and day 13 (or Day x -1) also meets the definition of alleviation, then it is considered as confirmed. One missing day is allowed for the confirmation of Day 14 or last assessment, i.e if day 13 (or Day x-1 ) is missing and Day 12 (or Day x-2) meets the definition of alleviation, then it is considered as confirmed.

Examples:

Example	Day														Alleviation for a symptom on day	
	1	2	3	4	5	6	7	8	9	10	11	12	13	14		
1	2	2	2	1	1	1	0	0	0	0	0	0	0	0	4	baseline 2 or higher needs to be 1 or 0
2	2	2	2	0	1	1	0	0	0	0	0	0	0	0	4	baseline 2 or higher needs to be 1 or 0
3	2	2	2	0	2	1	1	0	0	0	0	0	0	0	6	day 4 is not confirmed
4	3	2	2	1	1	1	0	2	1	1	0	0	0	0	4	still on day 4 if worsen after confirmation
5	1	1	1	0	0	0	1	0	1	1	0	0	0	0	4	Worsening on day 7
6	1	1	1	1	0	0	0	0	0	0	0	0	0	0	5	baseline 1 needs to be 0
7	2	2	2	1	.	1	0	0	0	0	0	0	0	0	4	allow one missing
8	2	2	2	1	.	.	1	1	.	0	0	0	0	0	7	day 4 is not confirmed if there are two or more days' response missing, re-start the check for confirmation
9	2	2	2	2	2	2	2	2	4	2	2	2	2	1	14	censor
10	2	2	2	2	2	2	2	2	2	2	2	2	1	.	13	censor
11	2	2	2	2	2	2	2	2	2	2	2	1	1	1	13	Confirmed on day 13 and 14
12	2	2	2	2	2	2	2	2	1	.	.	.	.	.	9	censor
13	2	2	2	2	2	2	2	2	1	1	.	.	.	.	9	Confirmed on day 9 and 10

Yellow - Confirmed alleviation, Tan - Not confirmed, Blue - Worsening

### 3. Alleviation of baseline symptoms for a participant

The alleviation status for a participant at each visit is

- Yes, if all confirmed baseline symptom alleviation status are Yes.
- if > 25% of symptoms are missing, then alleviation status is No, else ignore missing.
- No, if any baseline symptom alleviation status is No.

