## 6.2. Secondary Endpoints

The other endpoints of interest include:

- Composite endpoint of COVID-19 related MAVs (medical visits attended in person by the participant and a health care professional) or all cause death by Day 28
- All-cause mortality by Day 28
- Proportion of participants hospitalized (COVID-19 related) by Day 28
- Composite endpoint of COVID-19 related hospitalization (defined as at least 24 hours of acute care) or all-cause death by Day 14
- Composite endpoint of COVID-19 related MAVs (medical visits attended in person by the participant and a health care professional) or death by Day 14
- Time-weighted average change in SARS-CoV-2 viral load from baseline to Day 7
  - The time-weighted average change from baseline to study Day 7 (DAVG7) in SARS-CoV-2 viral load (log10 copies/mL) is defined as the time-weighted average between the first postbaseline value through the last available value up to Day 7 minus the baseline value in SARS-CoV-2 viral load (log10 copies/mL). DAVG7 is calculated using the trapezoidal rule and the area-under-the-curve (AUC) concept as follows:

$$DAVG_7 = \frac{AUC_{t_1-t_7}}{(t_7 - t_1)} - Y_0$$

The AUC between  $t_1$  and  $t_n$  in a time (ie, day) versus SARS-CoV-2 viral load (log10 copies/mL) plot is calculated as

$$AUC_{t_1-t_n} = \sum_{i=1 \text{ to } (n-1)} \frac{1}{2} (Y_i + Y_{i+1}) \times (t_{i+1} - t_i)$$

Where  $Y_i$  is the SARS-CoV-2 viral load (log10 copies/mL) at time  $t_i$ ,  $t_1$  is the first postbaseline time, and  $Y_0$  is the baseline SARS-CoV-2 viral load (log10 copies/mL).

- For subject with SARS-CoV-2 viral load data only available up to Day  $x$  ( $x < 7$ ),  
$$DAVG_7$$
 is defined as  $DAVG_7 = \frac{AUC_{t_1-t_x}}{(t_x - t_1)} - Y_0$
- If baseline viral load is missing or there is no post-baseline data, then the participant will be excluded from the analysis. If there is one post-baseline data value  $Y_i$ ,  $DAVG_7 = Y_i - Y_0$ . If a participant receives additional COVID-19 treatments (see [Appendix 2](#)), the viral load from the start of additional treatment will be excluded.
- Time to alleviation (mild or absent) of baseline COVID-19 symptoms as reported on the COVID-19-adapted FLU-PRO Plus
  - The alleviation of baseline COVID-19 symptoms, i.e. overall alleviation of all symptoms scored 1 or higher at baseline for each participant, is defined as:

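### When diary items are left blank, SAP Appendix 2 item 18.3 can date alleviation of all baseline symptoms on a day when the one unresolved symptom was simply not answered

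*SAP*

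**What the plan says.** SAP Section 6.2 defines the endpoint as "overall alleviation of all symptoms scored 1 or higher at baseline for each participant", held for two consecutive days and dated at the "First Date of the two consecutive dates achieving alleviation - First dose Date + 1". It makes no allowance for unanswered items.

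The programming rules are in SAP Appendix 2, item 18 (its numbered parts are cited here as 18.1 to 18.4).

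- **18.2, one symptom.** A symptom must fall to its threshold and be confirmed at a second visit. For confirmation, "one missing day between two visits (that meets the alleviation definition) is allowed"; two or more missing days restart the check. At the last assessment, confirmation looks backward.
- **18.3, the participant, at each visit.** The status is "Yes, if all confirmed baseline symptom alleviation status are Yes". A single symptom that is observed and not alleviated blocks this: the status is "No, if any baseline symptom alleviation status is No". For unanswered items the instruction is "if > 25% of symptoms are missing, then alleviation status is No, else ignore missing".
- **18.4, the event date.** "First day of participant level alleviation status equals Yes".

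Item-level blanks are foreseen: the FLU-PRO scoring table in Appendix 2, item 17, lets domain scores be computed with some items unanswered. SAP Section 6.2.1 plans Kaplan-Meier estimates, a log-rank test and a Cox hazard ratio for this endpoint. SAP Section 3.5 makes every efficacy endpoint other than the primary exploratory, tested at the two-sided 5% level without multiplicity adjustment.

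**The concern.** Item 18.2 bridges a missing day only when the visits on both sides of it meet the definition. Item 18.3 does not repeat that condition. An unanswered symptom simply leaves the day's assessment, provided no more than 25% are missing, whatever it scored the day before and the day after. If it was the only symptom holding the participant back, its absence turns the day into a Yes, and 18.4 makes that day the event.

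Three results are then wrong for that participant:

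- The alleviation date is too early.
- The unresolved score on the following day counts as worsening after alleviation under Section 6.2.
- A participant whose symptom never resolves, and who should be censored, becomes an event.

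Section 6.2 and Appendix 2 then give different answers for the same diary, and the programmer has to choose between them.

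**Working it through.** **Inputs.** The rules are from SAP Appendix 2, items 18.1 to 18.4, and SAP Section 6.2. The questionnaire has 34 symptom items (18.1), so a participant has at most 34 baseline symptoms. No document gives an item non-response rate. Below, n is the number of baseline symptoms, k the number of days one symptom stays unresolved after all the others have resolved, and m the chance that an item is skipped on a given day.

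**Step 1: reproduce the plan's own examples.** Item 18 has 13 worked examples, all at symptom level; there is none for the participant-level rule. Coding 18.2 as written reproduces all five examples that contain a missing day (7, 8, 10, 12 and 13: Day 4, Day 7, censored Day 13, censored Day 9, Day 9). Over the whole table 12 of 13 agree. Example 11 codes to Day 12 against a printed Day 13. It has no missing day, does not bear on this point, and may be a conversion effect.

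**Step 2: when is a blank ignored?** One blank is ignored when 1/n ≤ 25%, so n ≥ 4 (1/4 = 25% is not more than 25%). With n = 2 (50%) or n = 3 (33%) the day is No. The number of items that can be ignored on one day is the integer part of 0.25n: 1 for n = 4 to 7, 2 for n = 10, and 8 for n = 34.

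**Step 3: test diary.** All baseline scores are 2, so 18.2 requires: "Symptom scored as 2 or higher at baseline are scored as 0 or 1 at postbaseline". All symptoms but one read 2 to Day 4, 1 on Day 5 and 0 afterwards. The remaining one reads 2 to Day 4, blank on Day 5, 2 on Days 6 to 9, 1 on Day 10, then 0.

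| Diary | Rule as written | Blank counts only if both neighbouring days meet the definition |
|---|---|---|
| n = 4, 5, 10 or 34 | Day 5 | Day 10 |
| n = 2 or 3 | Day 10 | Day 10 |
| n = 5, last symptom stays at 2 to Day 14 | Day 5 | censored Day 14 |

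With no blank, the diary in the first two rows gives Day 10. In the first and third rows the score of 2 on Day 6 also counts as worsening under the rule as written.

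**Step 4: would two participant-level Yes days be enough?** Only for a single blank. In the n = 5 diary, requiring them moves the event back to Day 10. With blanks on Days 5 and 6 and a symptom that never resolves, the event is still dated Day 5.

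**Step 5: frequency, on assumed skip rates.** Of the k lingering days, only the first k − 1 are followed by another unresolved day. With independent skips, the chance of at least one blank on those days is 1 − (1 − m)^(k−1).

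| | m = 1% | m = 2% | m = 3% |
|---|---|---|---|
| k = 5 | 1 − 0.99^4 = 3.9% | 1 − 0.98^4 = 7.8% | 1 − 0.97^4 = 11.5% |
| k = 7 | 1 − 0.99^6 = 5.9% | 1 − 0.98^6 = 11.4% | 1 − 0.97^6 = 16.7% |

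These apply to participants with n ≥ 4 and exactly one lingering symptom. They are not trial-wide rates.

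**Step 6: illustration over whole diaries.** Assume independent skips of 1% to 10% per day, all baseline scores 2, and each symptom resolving at 2 days plus an exponential time with mean 6 days. Among dated events, about 5% to 23% (n = 4) and 6% to 28% (n = 10) fall on a day when a skipped symptom reads unresolved the day before and the day after. These percentages depend entirely on the assumptions.

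**The case against.** **Appendix 2 already confirms over two days.** This stands. Item 18.3 asks for confirmed symptom statuses, and each is confirmed at two visits under 18.2. With no blanks, if every symptom is confirmed from day d, all meet the definition on d and d+1, which is the Section 6.2 event. A reader who sees only 18.4 might infer that the participant-level rule drops the two-day requirement altogether. The documents do not support that; the divergence is confined to missing items.

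**A narrower reading of missing.** Item 18.1 says a symptom's status is missing at all visits when every score from Day 2 onward is missing, and this is the only place that says when a status is missing. If 18.3 used the word in that sense, the 25% rule would cover only never-answered items, and an item unresolved on both sides of a blank would be No and block the event. The reading is possible, but 18.3 does not state it, and setting status at each visit points to blanks at that visit. If it was intended, the SAP still needs a sentence saying so.

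**Limited stakes.** The endpoint is secondary and exploratory, the trial is double-blind, the documents give no reason for blanks to differ by arm, and the primary endpoint is untouched. All of this stands and limits the weight of the point. It does not reconcile the two sections.

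**Conclusion.** The point holds for diaries with unanswered items. As written, 18.3 and 18.4 can date alleviation of all symptoms on a day when the only unresolved symptom was left blank, contrary to Section 6.2. It needs at least four baseline symptoms and every other baseline symptom confirmed as alleviated on that day. It also rests on reading missing in 18.3 as missing at the visit.

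The sure effects are some dates that are too early, some false worsening, and some censored participants turned into events. How many cannot be computed from the documents; the 3.9% to 11.5% for k = 5 is conditional on the assumed skip rates and on independent skips.

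Three stronger conclusions might be inferred and are not supported:

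- **That the hazard ratio is diluted.** The direction of any bias cannot be derived from the documents.
- **That every blank on a lingering day is contradicted on both sides.** A blank on the last lingering day dates the event one day early, but the next score is not unresolved. Counting that day would raise the k = 5, m = 3% figure from 11.5% to 14.1%.
- **That the whole symptom objective rests on this date.** Section 6.2 also lists worsening after alleviation, and Appendix 2 describes domain-level alleviation.

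**What to change.** In 18.3, replace the instruction to ignore missing items with a rule to this effect:

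- A baseline symptom that is blank at a visit but answered on other post-baseline days counts as alleviated at that visit only if the adjacent observed scores meet the 18.2 definition. At most one missing day is bridged, and 18.2's backward confirmation at the last assessment is kept. Otherwise its status at that visit is No.
- The 25% tolerance applies only to baseline symptoms with no post-baseline score at all, the case described in 18.1.
- The two consecutive days in Section 6.2 are the two days already used for symptom confirmation; no further confirmation day is added.

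The last sentence matters. Requiring two consecutive participant-level Yes days on top of 18.2 would in effect require three days. A complete diary with every symptom meeting the definition on Days 5 and 6 and one returning on Day 7 is alleviated on Day 5 under Section 6.2, but would fail such a rule.

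The cost is a few sentences in Appendix 2, a modest program change and ideally one participant-level worked example. Some dates move later and some events become censored. With two or three baseline symptoms, where one blank now forces a No, a properly bridged blank could move a date earlier. The change belongs before database finalization. SAP Section 1 requires any change made after the SAP is final to be documented in the study report.
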